The primary outcome, clearance rate, will be calculated by dividing the stone surface area by the clearance time. To compare the clearance rate between groups a mixed effects model will be used including treatment group as a fixed effect and site (hospital) as a random effect. Any demographics that were found to be unbalanced between groups may also be included in the model as covariates.

Device malfunctions will be recorded and summarized by treatment group. The proportion of cases experiencing device malfunctions will be compared between groups using Fisher's Exact test. All subject complications will be recorded and summarized using the Clavien Classification of Surgical Complications. The proportions of subjects experiencing complications will also be compared between groups using Fisher's Exact test. The number (and percent) of patients found to be stone free at 6-12 weeks post-op will be summarized and compared between groups using Fisher's Exact test.

The main analysis of the primary endpoint will be performed on the ITT dataset. Supportive analyses may be performed on the PP dataset. All reporting and analysis of adverse events and complications will be done using the SA data set.

Control of Systematic Error/Bias

To minimize selection bias there will be a single randomization schedule managed at the lead investigative site. Upon subject enrollment, all participating sites will contact the main site for experimental group randomization. The randomization will be a permuted block randomization that will help ensure a reasonable balance of group assignment throughout the study enrollment period.

Number of Subjects per Investigative Site

The maximum number of subjects for any single site is 85.

Data Management

Data Collection, Processing, and Review

Subject data will be recorded in a limited access, secure, web-based electronic data capture (EDC) system called REDCap. REDCap is designed to comply with HIPAA regulations. REDCap is not 21 CFR Part 11 compliant; however, this data will not be submitted to the FDA as it is part of a post-market study comparing two commercialized devices for their cleared intended uses.

The conduct of clinical studies pertaining to the use of electronic records and signatures. Database backups are performed regularly.

The Investigator provides his/her electronic signature on the appropriate electronic case report forms (eCRFs) in compliance with local regulations. A written signature on printouts of the eCRFs must also be provided if required by local regulation. Changes to data previously submitted to the sponsor require a new electronic signature by the Investigator acknowledging and approving the changes.

Visual and/or electronic data review will be performed to identify possible data discrepancies. Manual and/or automatic queries will be created in the EDC system and will be issued to the site for appropriate response. Site staff will be responsible for resolving all queries in the database.

Data Retention

The Principal Investigator or his/her designee or Investigational site will maintain, at the investigative site, all essential study documents and source documentation that support the data collected on the

study subjects in compliance with regulatory guidelines. Documents must be retained for at least 2 years after the last approval of a marketing application or until at least 2 years have elapsed since the formal discontinuation of the clinical investigation of the product.

Data Safety Review

Individual Investigators will conduct continuous review of data and patient safety. Summaries submitted to the lead site should include review of data, the number of patients, significant adverse events as described in the risks, and responses observed. A combined summary for all sites will be submitted half way through enrollment (50 subjects) and at the completion of enrollment (100 subjects) for review by the DSMC.

Amendments

If a protocol revision is necessary which affects the rights, safety or welfare of the subject or scientific integrity of the data, an amendment is required. Appropriate approvals (e.g., IRB) of the revised protocol must be obtained prior to implementation.

Deviations

An Investigator must not make any changes or deviate from this protocol, except to protect the life and physical well-being of a subject in an emergency. An investigator shall notify the sponsor and the reviewing IRB of any deviation from the investigational plan to protect the life or physical well-being of a subject in an emergency, and those deviations which affect the scientific integrity of the clinical investigation. Such notice shall be given as soon as possible, but no later than 5 working days after the emergency occurred, or per prevailing local requirements, if sooner than 5 working days.

All deviations from the investigational plan, with the reason for the deviation and the date of occurrence, must be documented and reported to the sponsor. Sites may also be required to report deviations to the IRB/EC, per local guidelines and government regulations.

Deviations will be reviewed and evaluated on an ongoing basis and, as necessary, appropriate corrective and preventive actions (including IRB notification, site re-training, or site discontinuation/termination) will be put into place by the sponsor.

Device/Equipment Accountability

The study devices/equipment shall be securely maintained, controlled, and used only in this clinical study.

Compliance

Statement of Compliance

This study will be conducted in accordance with ICH Guidelines, Good Clinical Practices ISO 14155, ethical principles that have their origins in the Declaration of Helsinki, and pertinent individual country laws and regulations. The study shall not begin until the required approval/favorable opinion from the IRB authority has been obtained. Any additional requirements imposed by the IRB shall be followed, if appropriate.

Investigator Responsibilities

The Principal Investigator of an investigational site is responsible for ensuring that the study is conducted in accordance with the Clinical Study Agreement, the clinical investigation plan, ISO 14155, ethical principles that have their origins in the Declaration of Helsinki, any conditions of approval imposed by the reviewing IRB, and prevailing local and/or country laws and/or regulations, whichever affords the greater protection to the subject.

The Principal Investigator's responsibilities include, but are not limited to, the following.

- Prior to beginning the study, sign the Clinical Study Agreement and comply with the Investigator responsibilities as described in such Agreement.
- Prior to beginning the study, sign the Protocol Signature page documenting his/her agreement to conduct the study in accordance with the protocol.
- Provide his/her qualifications and experience to assume responsibility for the proper conduct of the study and that of key members of the site team through up-to-date curriculum vitae or other relevant documentation and disclose potential conflicts of interest, including financial, that may interfere with the conduct of the clinical study or interpretation of results.
- Make no changes in or deviate from this protocol, except to protect the life and physical well-being of a subject in an emergency; document and explain any deviation from the approved protocol that occurred during the course of the clinical investigation.
- Create and maintain source documents throughout the clinical study and ensure their availability with direct access during monitoring visits or audits; ensure that all clinical-investigation-related records are retained per requirements.
- Ensure the accuracy, completeness, legibility, and timeliness of the data reported to the sponsor in the CRFs and in all required reports.
- Record, report, and assess (seriousness and relationship to the device/procedure) every adverse event as applicable per the protocol and observed device deficiency.
- Allow and support regulatory authorities and the IRB/EC when performing auditing activities.
- Ensure that informed consent is obtained in accordance with applicable laws, this protocol and local IRB/EC requirements.
- Provide adequate medical care to a subject during and after a subject's participation in a clinical study in the case of adverse events, as described in the ICF.

- Inform the subject of the nature and possible cause of any adverse events experienced.
- Inform the subject of any new significant findings occurring during the clinical investigation, including the need for additional medical care that may be required.
- Provide the subject with well-defined procedures for possible emergency situations related to the clinical study, and make the necessary arrangements for emergency treatment, including decoding procedures for blinded/masked clinical investigations, as needed.
- Ensure that clinical medical records are clearly marked to indicate that the subject is enrolled in this clinical study.
- Ensure that, if appropriate, subjects enrolled in the clinical investigation are provided with some means of showing their participation in the clinical investigation, together with identification and compliance information for concomitant treatment measures (contact address and telephone numbers shall be provided).
- Inform, with the subject's approval or when required by national regulations, the subject's personal physician about the subject's participation in the clinical investigation.
- Make all reasonable efforts to ascertain the reason(s) for a subject's premature withdrawal from clinical investigation while fully respecting the subject's rights.
- Ensure that an adequate investigation site team and facilities exist and are maintained and documented during the clinical investigation.
- Ensure that maintenance and calibration of the equipment relevant for the assessment of the clinical investigation is appropriately performed and documented, where applicable.

Delegation of Responsibility

When specific tasks are delegated by an investigator, including but not limited to conducting the informed consent process, the Principal Investigator is responsible for providing appropriate training and adequate supervision of those to whom tasks are delegated. The investigator is accountable for regulatory violations resulting from failure to adequately supervise the conduct of the clinical study.

Institutional Review Board/Ethics Committee

The protocol and informed consent document must have the approval of a properly constituted committee ("Institutional Review Board" / "Ethics Committee") responsible for approving clinical trials. The signed IRB/EC approval letter must identify the documents approved (i.e., list the Investigator's name, the protocol title, and date of approval, and informed consent document). A copy of the approval of the protocol (or permission to conduct the study) and Informed Consent Form, must be received by the sponsor before recruitment of subjects into the study and shipment of investigational product/equipment. Prior approval must also be obtained for other materials related to subject recruitment or which will be provided to the subject.

Annual IRB/EC approval and renewals will be obtained throughout the duration of the study as required by local/country or IRB/EC requirements. Copies of the Investigator's reports and the IRB/EC continuance of approval must be provided to the sponsor.

Potential Risks and Benefits

Anticipated Adverse Device Effects

The following adverse events (AEs) are considered anticipated during percutaneous nephrolithotomy procedures and are reflected in the commercial instructions for use (IFU) for each lithotripsy device:

- Infection
- Bleeding
- Damage to the kidney or surrounding organs
- Other adverse events associated with anesthesia

Each participating site is responsible for recording AEs and classifying them based on the below Clavien Classification system:

Clavien Classification of Surgical Complications

All adverse events that occur intra-operatively or within the 30 day postoperative period will be assessed using the Clavien Classification of Surgical Complications:

Grade I: Any deviation from the normal post-operative course without the need for pharmacological treatment or surgical, endoscopic, and radiological interventions.
Allowed therapeutic regimens are: drugs as antiemetics, antipyretics, analgesics, diuretics, electrolytes, and physiotherapy. This grade also includes wound infections opened at bedside.

Grade II: Requiring pharmacological treatment with drugs other than such allowed for Grade I complications. Blood transfusions and total parenteral nutrition are also included.

Grade III: Requiring surgical, endoscopic or radiological intervention.
Grade IIIa: Intervention not under general anesthesia
Grade IIIb: Intervention under general anesthesia

Grade IV: Life-threatening complication (including CNS complications) requiring IC/ICU management.
Grade IVa: Single organ dysfunction (including dialysis)
Grade IVb: Multi-organ dysfunction

Grade V: Death of a patient

Suffix “d”: If the patient suffers from a complication at the time of discharge the suffix “d” (for disability) is added to the respective grade of complication. This label indicates the need for a follow-up to fully evaluate the complication.

Termination of Study Participation by the Investigator or Withdrawal of IRB/ EC Approval

Any investigator, or IRB/ EC in this Study may discontinue participation in the study or withdrawal approval of the study, respectively. Investigators, associated IRBs/ECs, and regulatory authorities, as applicable, will be notified in writing in the event of these occurrences.

Abbreviation	Definition
AE	Adverse Event
CA	Competent Authority
CRF / eCRF	Case Report Form / Electronic Case Report Form
CRO	Clinical Research Organization
CT	Computed Tomography
EBL	Estimated Blood Loss
EC	Ethics Committee
EDC	Electronic Data Capture
FDA	Food and Drug Administration
GCP	Good Clinical Practice
HIPAA	Health Insurance Portability and Accountability Act
ICF	Informed Consent Form
ICH	International Conference on Harmonization
ICMJE	International Committee of Medical Journal Editors
IFU	Instructions for Use
IRB	Institutional Review Board
ISO	Internal Organization for Standardization
ITT	Intent-to-Treat
KUB	Kidney, Ureter, and Bladder

NEMA	National Electrical Manufacturers Association
OD	Outer Diameter
PP	Per Protocol
SA	Safety Analysis
SAE	Serious Adverse Event
UADE	Unanticipated Adverse Device Effect
USA	United States of America

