Additional Endpoints	
Additional endpoints include the following:
 
 1. Device malfunctions 2. All complications measured by the Clavien Classification of Surgical Complications 3. Stone free status as defined by the presence or absence of stone material on postoperative CT imaging and at final follow up 
 • Stone free status must be assessed postoperative day 1 by CT scan.
Method of Assigning Patients to Treatment	
The patients will be block randomized 1:1 to either stone removal with the Trilogy or the ShockPulse –SE device.

Follow-up Schedule	
 1. Baseline (Clinic Visit) – within 3 months prior to surgical procedure 2. Procedure (Hospital Visit) 
 • Stone free status may be assessed at this time by CT scan on Postoperative day 1 3. 6-12 Week Follow-up Visit (Clinic Visit) 
 • Stone free status may be assessed at this time by KUB scan and/or ultrasound, or CT scan 4. End of Study 
 • End of study will be reached after completion of the 6-12 Weeks Follow-up Visit, subject withdrawal or lost to follow-up, whichever occurs first.
Study Duration	
It is anticipated that this study will take 12 months to complete once IRB approval is obtained at all participating locations.

Key Inclusion Criteria	
 1. ≥ 18 years of age 2. Stone burden ≥ 1.5 cm as measured on preoperative CT scan 3. Patient is scheduled to undergo a percutaneous nephrolithotomy procedure 4. Willing and able to provide informed consent
Key Exclusion Criteria	
 1. Pregnant 2. Active urinary tract infection 3. Prior shock wave lithotripsy within 3 months of study procedure 4. Multiple percutaneous access sites are anticipated 5. Unable or unwilling to provide informed consent
Statistical Methods	
Primary Statistical Hypothesis	We hypothesize that the Trilogy will increase the stone clearance rate by 25% compared to the Shockpulse-SE
Statistical Test Method	Outcomes between treatment groups will be assessed using a t-test to compare means. Values of $p \leq 0.05$ will be considered significant.

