To compare the performance, as measured by the stone clearance rate at time of percutaneous nephrolithotomy, of the ShockPulse-SE Lithotripsy System to the Trilogy Lithotrite.

Study Endpoints

Primary Endpoint

Stone clearance rate defined as the kidney stone surface area measured by preoperative computed tomography (CT) scan divided by the time to remove the targeted stone burden.

Time to remove the targeted stone burden is measured at time the lithotripter unit starts fragmenting the stone to time all fragments are removed from the kidney based on visual inspection. This is prior to final visual inspection of the kidney with a flexible nephroscope.

Additional Endpoints

1. Device malfunctions
2. All complications measured by the Clavien Classification of Surgical Complications

Stone free status as defined by the presence or absence of stone material on postoperative day 1 CT imaging

This study is a post-market, prospective, randomized, multicenter, 2-arm, comparative trial.

Scale and Duration

A total of 100 subjects will be enrolled and treated at 3 study sites across the USA. Each subject will be followed for approximately 6-12 weeks after the study procedure. It is anticipated for the entire study to last approximately 12 months.

***All sites will perform 10 independent PCNL cases, outside of the study period, using the Trilogy lithotrite to become accustomed with the device prior to enrolling patients.**

Treatment Assignment

The patients will be block randomized 1:1 to either stone removal with the Trilogy or the ShockPulse–SE device. All randomization will occur at the central study site via computer randomization by the statistician to limit selection bias.

Justification for the Study Design

This study will compare performance of two devices for the treatment of large renal calculi. The study has been designed as a prospective, multi-centric, randomized, comparative study. The intent of this design is to minimize bias and to allow for statistical comparison of the two treatment groups.

Subject Selection

Study Population and Eligibility

Patients who meet all of the inclusion criteria and none of the exclusion criteria will be considered for inclusion in the study.

Inclusion Criteria

1. ≥ 18 years of age
2. Stone burden ≥ 1.5 cm as measured on preoperative CT scan
3. Patient is scheduled to undergo a percutaneous nephrolithotomy procedure
4. Willing and able to provide informed consent

Exclusion Criteria

1. Pregnant

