 - 3: A patient with severe systemic disease
 - 4: A patient with severe systemic disease that is a constant threat to life
- Number and location of access sites for lithotripsy procedure
- Total procedure time as measured in minutes from induction of anesthesia to end of anesthesia
 - **Please ensure these time points exists in the subject's source documentation**
- Time to clearance of targeted stone burden as measured in minutes
 - Start time: When the investigator begins to use the lithotriptor on the targeted stone
 - Stop time: When the investigator has cleared all fragments and prior to final inspection of the kidney with the flexible nephroscope
 - **Please ensure these time points exists in the subject's source documentation**
- Use of other intracorporeal lithotripsy devices including laser
- Settings utilized for each lithotripter device
- Stone Free Status
 - Assessed by CT scan performed postoperative day 1.
- Estimated blood loss (EBL)
- Device malfunctions
- Adverse events

2.1.1.Post-operative Data:

- Length of hospitalization measured in days
- Need for blood transfusion
- Assessment of nephrostomy tube
- Adverse events
- Stone Free Status
 - Date of imaging study should be provided.
- Stone analysis
- Stone culture results
- Post-operative laboratory data
 - Serum creatinine (mg/dl)
 - Hemoglobin (g/dl)
 - Hematocrit (%)

- Na (mEq/l)

6-12 Week Follow-up Visit (Clinic Visit):

The following data will be captured during the 6-12 Week Follow-up Visit:

- Stone Free Status
 - Date of imaging study should be provided. Either a CT or KUB and/or Ultrasound is required prior to or during the 6-12 Week Follow-up Visit.
- Adverse events

Unscheduled Visit (Clinic Visit):

Unscheduled visits may be performed between visits required by the protocol as deemed necessary by the investigator. Data for unscheduled visits will be captured on the Adverse Event case report form (CRF).

End of Study

End of study will be reached after completion of the 6-12 Week Follow-up visit, subject withdrawal, or lost to follow-up, whichever occurs first.

Source Documents

Source documents are the patient records maintained at the study site. In most cases, the source documents will be the physician's or hospital's patient chart. In some cases, the source documents may be electronic. In both cases, the information captured in the CRF must match the information in the chart or electronic source document.

Statistical Considerations

Endpoints

Primary Endpoint

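### The only planned stone-free comparison, at 6-12 weeks, mixes clearance by the device with clearance by any later stone procedure, because no dedicated item records such procedures and no scoring rule covers them

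*Combined protocol and SAP*

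**What the plan says.** Statistical Methods plans one stone-free comparison: "The number (and percent) of patients found to be stone free at 6-12 weeks post-op will be summarized and compared between groups". The method named for it is Fisher's exact test. The section sets no condition on how the patient became stone free and names no analysis set for this endpoint; the ITT statement there concerns the primary endpoint.

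The endpoint is described differently elsewhere. Study Endpoints has "Stone free status as defined by the presence or absence of stone material on postoperative day 1 CT imaging". The synopsis has "Stone free status as defined by the presence or absence of stone material on postoperative CT imaging and at final follow up". Footnote 1 of the data collection table makes the day 1 CT compulsory, and the procedure-visit data list repeats it. No between-group test of the day 1 result is planned.

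For the final visit, Study Methods begins "The following data will be captured during the 6-12 Week Follow-up Visit" and lists two items, stone-free status and adverse events. On imaging: "Either a CT or KUB and/or Ultrasound is required prior to or during the 6-12 Week Follow-up Visit". The post-operative list covers hospital stay, transfusion, nephrostomy tube, adverse events, stone-free status, stone analysis and culture, and laboratory values. Neither list, nor the schedule table, has an item for a further stone procedure. The nearest item, "Use of other intracorporeal lithotripsy devices including laser", stands under intraoperative data and so describes the index operation. For visits in between: "Data for unscheduled visits will be captured on the Adverse Event case report form (CRF").

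**The concern.** The day 1 CT makes residual stone known weeks before the assessment that is analysed. A patient with residual stone on day 1 may have a second procedure and be clear by 6-12 weeks. Read literally, Statistical Methods scores that patient the same as one cleared at the index operation.

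If one device leaves more residual stone, its arm has more patients who could be retreated. Equal retreatment practice then pulls the two 6-12 week rates together and can hide a real device difference. The documents describe no blinding of surgeons or assessors, so retreatment practice could also differ by arm, which could create or reverse a difference. At stake is what the trial can say about stone-free status as a property of the lithotripter. The primary endpoint, clearance rate, is fixed during the operation and is not touched.

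**Working it through.** **The plan's own figure.** The sample size concerns clearance rate only: effect size 0.7, two-sided alpha 0.05, power 90%, 44 per arm. The two-sample t-test calculation gives 43.87, rounded up to 44, so it reproduces. The documents give no expected rate, power or sample size for stone-free status. The 50 per arm below is the planned enrolment.

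**What the data can separate.** Cross-tabulating day 1 CT status against 6-12 week status identifies every patient who went from residual stone to stone free. Three explanations remain for such a patient:
- *Retreatment:* no dedicated item. It is captured only if reported as an adverse event, graded by Clavien only within 30 days, and not linked to stone-free scoring.
- *Spontaneous passage:* no item.
- *Residual fragment missed at follow-up:* possible because KUB and/or ultrasound may replace CT.

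The data show that a patient converted, but not why.

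**Size, under assumed rates.** Let p be the proportion cleared by the device alone and k the share of residual-stone patients cleared by retreatment. The 6-12 week rate is p + (1 - p)k. With equal k in both arms, the difference is (p2 - p1)(1 - k). Assume p1 = 0.60 and p2 = 0.80. For example, at k = 0.2 the rates are 0.60 + 0.40 × 0.2 = 0.68 and 0.80 + 0.20 × 0.2 = 0.84. Power is for the exact two-sided Fisher test at 0.05, 50 per arm, by enumeration.

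| k | Rates at 6-12 weeks | Difference (points) | Fisher power |
|---|---|---|---|
| 0 | 60% vs 80% | 20 | 52% |
| 0.05 | 62% vs 81% | 19 | 48% |
| 0.1 | 64% vs 82% | 18 | 45% |
| 0.2 | 68% vs 84% | 16 | 39% |
| 0.4 | 76% vs 88% | 12 | 26% |
| 0.6 | 84% vs 92% | 8 | 14% |

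**Unequal retreatment.** Take equal devices, 70% in each arm, and k = 0.75 vs 0.25. The rates become 0.70 + 0.30 × 0.75 = 92.5% and 0.70 + 0.30 × 0.25 = 77.5%. That is a 15-point difference with no device effect, significant in 45% of trials. This is a deliberately extreme case.

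**The case against.** Three stronger readings are tempting, and the documents do not support them.

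- *A reader might infer that the dataset cannot tell a retreated patient from one cleared at surgery.* It partly can. Day 1 CT status is required for every patient, so a patient with residual stone on day 1 is recorded as such. Only the cause of a later conversion is lost.
- *A reader might infer that later procedures are not recorded at all.* Adverse events are collected after surgery, at unscheduled visits and at the final visit, and Clavien Grade III covers surgical, endoscopic and radiological intervention. This capture is real but incomplete. A procedure for residual stone need not be reported as an adverse event, and the 30-day Clavien window ends before the 6-12 week assessment.
- *A reader might infer that the planned comparison is an error in itself.* Stone free at 6-12 weeks regardless of later procedures is a coherent outcome. Replacing it by one that counts every retreated patient as a failure would be partly a preference, and would put an unblinded retreatment decision inside the endpoint.

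It is also fair to say that this is one of three additional endpoints, with no hypothesis of its own; that the size rests wholly on assumed rates; and that even without retreatment the illustrative power is only 52%. Analysing the day 1 CT, as Study Endpoints defines the outcome, would give a device comparison that later retreatment cannot affect. All of this stands. It limits the point but does not remove it: no day 1 comparison is planned, and adding one would still leave the 6-12 week result open to more than one explanation.

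**Conclusion.** The point holds as a gap in recording and prespecification for an additional endpoint. As planned, the 6-12 week comparison measures device plus any retreatment, and the data collected cannot reliably show how much is due to each. That retreated patients would count as stone free follows from the unconditional wording; the plan does not say so expressly.

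The textual finding is firm. The size is not, because the documents give neither stone-free nor retreatment rates. On the 60% vs 80% assumption the loss runs from 1 point of difference at k = 0.05 to 12 points at k = 0.6. If retreatment is rare, little is lost; if it is common or differs by arm, the comparison says little about the device. The primary analysis and its 44 per arm are unaffected. The change is worth making because it is cheap and the information cannot be reliably rebuilt afterwards.

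**What to change.** 1. On the post-operative, unscheduled-visit and 6-12 week CRFs, add one item: any further stone procedure on the study kidney since the index operation, with type, date, and whether planned or unplanned.
2. In Statistical Methods, prespecify a comparison of stone free at 6-12 weeks without a further stone procedure. Show it beside stone free regardless of retreatment, and report the proportion retreated by arm.
3. Read both lines with the day 1 CT result by arm, which later retreatment cannot affect.

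The cost is one CRF item and a few sentences in the analysis section. The rates on the retreatment-free line will be lower. That line also depends on an unblinded decision to retreat, which is why both lines are reported and neither stands alone. The change concerns recording and scoring only and sets no rule on whether or when patients are retreated.

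### Stone-free status is defined on the postoperative day 1 CT, but the plan analyses it only at 6-12 weeks, where the imaging may be CT, KUB or ultrasound

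*Combined protocol and SAP*

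**What the plan says.** All references are to the combined protocol and SAP.

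- **Study Endpoints, Additional Endpoints:** "Stone free status as defined by the presence or absence of stone material on postoperative day 1 CT imaging".
- **Synopsis, Additional Endpoints:** "Stone free status as defined by the presence or absence of stone material on postoperative CT imaging and at final follow up". A sub-bullet makes the day 1 CT mandatory.
- **Synopsis, Follow-up Schedule:** "Stone free status may be assessed at this time by CT scan on Postoperative day 1", which is permissive.
- **Data Collection table, footnote 1:** the day 1 CT assessment is mandatory.
- **Procedure visit, Intraoperative Data:** stone-free status is listed as a data item, "Assessed by CT scan performed postoperative day 1".
- **6-12 Week Follow-up Visit:** "Either a CT or KUB and/or Ultrasound is required prior to or during the 6-12 Week Follow-up Visit".
- **Statistical Considerations, Additional Endpoints:** the endpoint refers to postoperative imaging in general. A sub-bullet then ties it to CT with the garbled timing *prior POD #1*.
- **Statistical Considerations, Statistical Methods:** the only stone-free analysis is the number and percent of "patients found to be stone free at 6-12 weeks post-op will be summarized and compared between groups", by Fisher's exact test.

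Statistical Methods assigns the ITT set to the primary endpoint and the safety set to adverse events and complications. It assigns no set to stone-free status.

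**The concern.** An analyst who followed Statistical Methods exactly would test a later time point, on possibly mixed imaging, and would never tabulate the endpoint that Study Endpoints defines. The other two additional endpoints, device malfunctions and complications, each have a named summary and test.

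The day 1 result matters because of how the primary rate is built. Its numerator is the pre-operative stone area. Its clock runs "to time all fragments are removed from the kidney based on visual inspection", and the procedure section sets the stop time as "When the investigator has cleared all fragments and prior to final inspection of the kidney with the flexible nephroscope". Stone that the investigator does not see at that moment neither lengthens the time nor reduces the numerator. A reader comparing the two devices on speed will want to know how much stone remained. The day 1 CT is the only stone-free assessment with a fixed modality and a fixed day. It is an indirect check: it shows what was left after the whole procedure.

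Without a plan, three choices could be made after the data are seen: whether to report the day 1 result, in which subjects, and how prominently.

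**Working it through.** **Step 1. Match definition to analysis.**

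| Stone-free assessment | Defined as endpoint | Collected | Planned summary | Planned test |
|---|---|---|---|---|
| Day 1, CT only | Study Endpoints; synopsis (as postoperative CT); Statistical Considerations (garbled timing) | Yes, Intraoperative Data | None | None |
| 6-12 weeks, CT or KUB and/or ultrasound | Synopsis (final follow-up) | Yes, 6-12 Week Follow-up Visit | Number and percent | Fisher's exact |

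Two other sentences might be thought to cover day 1. The synopsis test statement compares means by t-test and does not name this binary endpoint. The summaries for the DSMC under Data Safety Review are part of safety review, not a comparison of devices on an endpoint. Neither fills the empty cells.

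**Step 2. The plan's own sample size, for context.** Inputs from Sample Size: effect size 0.7, two-sided alpha 0.05, power 90%. The normal approximation gives 2 × (1.960 + 1.282)² / 0.7² = 42.9, so 43 per group. The noncentral t calculation gives 43.87, so 44, which is the stated figure. Power is 90.1% at 44 per group and 93.4% at 50. These figures concern the clearance rate only; nothing in the documents sizes the trial for stone-free status.

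**Step 3. How precise a day 1 comparison could be.** No stone-free rate is given, so only a worst case can be stated. The Wald 95% half-width for a difference of two proportions is largest when both are 50%:

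- 50 per arm (all enrolled subjects have a CT): 1.96 × √(2 × 0.25 / 50) = 0.196
- 44 per arm: 1.96 × √(2 × 0.25 / 44) = 0.209

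The 44 is the primary endpoint's required number, borrowed here for illustration. It is not a floor for the number of day 1 CTs. The same bounds apply to the 6-12 week comparison.

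**Step 4. Power of Fisher's exact test, 50 per arm, under assumed rates.** The lower rate is assumed to be 50%, 60%, 70% or 80%. Power for a 10-point difference is 13.4%, 13.2%, 15.5% and 19.5% respectively. For a 20-point difference it is 46.3%, 51.5%, 64.0% and 95.2%, the last being 80% against 100%.

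**Step 5. Multiplicity cost.** Statistical Methods already has three between-device Fisher tests on additional endpoints (malfunctions, complications, 6-12 week stone-free). If the tests were independent at 0.05, the chance of at least one false positive would be at most 1 − 0.95³ = 14.3% now and 1 − 0.95⁴ = 18.5% with a fourth. Independence will not hold, because the two stone-free tests use the same patients. Whatever the dependence, the ceilings are 3 × 0.05 = 15% and 4 × 0.05 = 20%.

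**The case against.** The strongest reply is that the synopsis names final follow-up, so the 6-12 week test does analyse a stated part of the endpoint. That is correct. The gap is one of two stone-free time points, and the mismatch is complete only against the wording in Study Endpoints. On either wording, the day 1 CT part has no analysis.

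A second reply is that counts, percents and a confidence interval would close the reporting gap without another p-value. That has force. Fisher's test is proposed only for consistency with the other binary endpoints.

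Two stronger readings are tempting, and the documents do not support either.

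- *The day 1 CT directly tests whether a faster rate was bought with more residual stone.* The clock stops before the flexible nephroscope inspection, and the CT comes after it. Nothing excludes fragments being removed in between, and the procedure record allows for other lithotripters and laser. The primary time concerns the targeted stone, whereas the stone-free endpoint counts any stone material. The CT therefore reflects the whole procedure.
- *Anyone lost before the 6-12 week visit drops out of the only planned stone-free test.* Imaging obtained before the visit is accepted and no earliest date is set. The Withdrawal section also plans to seek follow-up from the patient's own physician and allows data gathered before withdrawal to be used. Whether such a subject has a value is not settled.

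**Conclusion.** The concern holds in this form: the day 1 CT stone-free result is defined as an endpoint, required and collected, but it has no planned summary and no planned comparison. The one stone-free analysis uses another time point and may rest on a different modality. This follows from the text and needs no assumption about rates.

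The consequence is limited. This is an additional endpoint, and the primary analysis and the 44 per group are unaffected. With worst-case half-widths of about 20 percentage points, and power below 20% for a 10-point difference under the rates assumed above, a day 1 comparison could miss differences of that size. A non-significant result would not show that the devices clear stone equally well. It is still worth fixing before data are analysed, because the change is small and removes choices that could otherwise follow the results.

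**What to change.** In Statistical Methods:

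1. Add a comparison of day 1 CT stone-free status by assigned device: number and percent per arm, the difference with a 95% confidence interval, and Fisher's exact test.
2. State that day 1 CT is the main stone-free result, in line with Study Endpoints, and that the 6-12 week comparison is a separate additional result. Label both as unadjusted and not sized for.
3. Define the population as randomized subjects who had the procedure and a day 1 CT, grouped by assigned device. Randomization takes place at screening and the procedure may follow up to 90 days after baseline, so some randomized subjects may never have surgery. Report the number per arm without a day 1 CT, and add a sensitivity analysis counting treated subjects without one as not stone free. Name the analysis set for the 6-12 week result too.
4. Describe the day 1 CT as an indirect check on residual stone after the whole procedure.

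Align the endpoint wording across the synopsis, Study Endpoints, Statistical Considerations (Additional Endpoints) and Statistical Methods. Reconcile *may* with *must* for the day 1 CT in the synopsis, and correct *prior POD #1*.

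The cost is one more unadjusted secondary comparison and a wording change, which may need the route under Amendments. Day 1 CT status is already a listed data item, so no new data are needed.
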